### **4.3 Justification for dose**

The rationale for testing the proposed clinical dose levels of UCB0599 180mg/day (90mg BID) and 360mg/day (180mg BID) in PD0053 is based on (1) the safety margin estimates comparing systemic exposures at the no observed adverse effect level (NOAEL) in monkey with human observed exposures in study participants with PD treated in UP0077, and (2) exposures that have shown pharmacological activity in transgenic mice that overexpress the human wildtype ASYN gene (SNCA) in the CNS.

Potential food effect as well as potential drug-drug interaction with itraconazole, a strong CYP3A4 inhibitor, were evaluated in UP0078 after UCB0599 single dose (180mg). Data from UP0078 confirmed that no food restriction is needed in PD0053. However, strong CYP3A4 inhibitors (and inducers) should not be co-administered with UCB0599 (see Section [6.5.2](#)).

#### **4.3.1 Safety-based dose levels**

UCB0599 exposure data in the most sensitive nonclinical species (monkey) are presented in [Table 4-1](#). The UCB0599  $C_{max}$  and  $AUC_{0-24h}$  following daily dosing of 60mg/kg/day for 39 weeks in male monkeys were 4090ng/mL and 28000h\*ng/mL, respectively. These PK parameters were used to determine the human safety margins, comparing nonclinical exposures with human observed exposures.

Across the dose range tested, UCB0599 behaved approximately linearly when relating dose and exposure; therefore, the projected equivalent  $AUC_{0-24h}$  at steady state at (180mg/day [90mg BID]) is 8072h\*ng/mL (mean  $AUC_{0-12h,ss}$  4036h\*ng/mL multiplied by 2; and at 360mg/day [180mg BID]) is 15908h\*ng/mL (mean  $AUC_{0-12h,ss}$  7954h\*ng/mL multiplied by 2) (Table 4-1).

**Table 4-1:  $C_{max}$  and AUC and unbound ( $C_{max(u)}$  and  $AUC_{(u)}$ ) UCB0599 exposures calculated on measured plasma protein binding in monkey or human plasma samples**

	$C_{max}$ ng/mL	$C_{max(u)}$ ng/mL	$AUC_{0-24h}$ h*ng/mL	$AUC_{0-24h(u)}$ h*ng/mL
Male monkey (39-week) (at 60mg/kg/day)	4090	200.4	28,000	1372.0
Observed human exposures (90mg BID, 180mg/day)	730	6.6	8072	72.6
Observed human exposures (180mg BID, 360mg/day)	1330	12	15,908	143.2

BID=twice per day

Note: Mean  $AUC_{0-24h}$ , calculated as 2x the measured  $AUC_{0-12h}$ , in UP0077 (Investigator Brochure Table 4-7 and 4-8).

Note: Plasma unbound fraction in monkeys and humans are 4.9% and 0.9%, respectively (Study NCD2777).

Comparing these human observed  $C_{max}$  and AUC parameters with the nonclinical data (Table 4-1) indicates that mean expected drug exposures remain below the observed mean NOAEL levels obtained in the 39-week monkey study. To further provide reassurance on the safety exposures, Table 4-1 also provides calculated unbound PK parameters, ie,  $C_{max(u)}$  and  $AUC_{(u)}$ , based on the concept of unbound drug being a pharmacologically active moiety. In monkey plasma, the mean bound percentage was  $95.1\pm3.4\%$  at  $37^\circ\text{C}$ . The protein binding in human plasma was  $99.1\pm0.1\%$  at  $37^\circ\text{C}$  (UCB study number NCD2777). Using the unbound fraction to convert to unbound (pharmacologically active) drug comparing the average exposure in human study participants vs the observed monkey exposure data, a safety margin of  $>15$  is to be expected on the basis of this calculation.

#### 4.3.2 Pharmacology-based dose levels

The projected exposures in humans at UCB0599 180mg/day (90mg BID) and 360mg/day (180mg BID) are predicted to correspond to efficacious CNS exposures in the transgenic mouse model overexpressing human wildtype ASYN gene (*SNCA*). Therefore, UCB0599 dose selection for UP0030 was projected to achieve systemic exposures in humans that were comparable to the efficacious exposures obtained in the pharmacological animal model (transgenic mice overexpressing *SNCA*), and, in particular, a range of exposures encompassed within those

expected after chronic administration at UCB0599 1mg/kg and UCB0599 5mg/kg. The AUC and  $C_{max}$  exposures (expressed as total and unbound) estimated after administration at UCB0599 1mg/kg were 308ng\*h/mL (unbound: 6.5h\*ng/mL) and 332ng/mL (unbound: 7.0ng/mL), respectively (Table 4-2). AUC and  $C_{max}$  exposures (total and unbound) estimated after administration at UCB0599 5mg/kg were 1648ng\*h/mL (unbound: 34.6h\*ng /mL) and 1317h\*ng/mL (unbound: 27.7ng/mL), respectively.

**Table 4-2: UCB0599 exposure at pharmacological dose**

Dose (mg/kg/day)	Gender	AUC0-24 (h*ng/mL)	<math>C_{max}</math> (ng/mL)	Unbound AUC0-24 (h*ng/mL)	Unbound <math>C_{max}</math> (ng/mL)
1	Male	308	332	6.5	7.0
5	Male	1648	1317	34.6	27.7

At UCB0599 180 or 360mg/day in UP0077, the projected exposure (AUC0-24h) in humans at these doses were 8072 and 15908h\*ng/mL, respectively (unbound: 72.6 and 143.2h\*ng/mL, respectively), and the  $C_{max}$  were 730 and 1330ng/mL, respectively (unbound: 6.6 and 12ng/mL, respectively), at steady state. This exposure covers the range of both  $C_{max}$  and AUC exposure in mice at the highest pharmacological dose of UCB0599 5mg/kg.

#### **4.4 End of study definition**

Participants are considered to have completed the study if they have completed all phases of the study, including the SFU Visit (30 days after the End of Treatment [EOT] Visit). Participants opting to enter PD0055 will not enter the SFU Period of PD0053, and are considered to have completed the study if they have completed all visits up to and including EOT.

The end of the study is defined as the date of the last visit of the last participant in the study.

### **5 STUDY POPULATION**

Prospective approval of protocol deviations to recruitment and enrollment criteria, also known as protocol waivers or exemptions, is not permitted.

#### **5.1 Inclusion criteria**

Participants are eligible to be included in the study only if all of the following criteria apply:

##### **Age**

1a. Study participant must be 40 to 75 years of age inclusive, at the time of signing the informed consent.

##### **Type of participant and disease characteristics**

2a. Study participant has PD, with a diagnosis made by a neurologist according to the 2015 Movement Disorder Society criteria within 2 years of Baseline Visit (including diagnosis during Screening).

---

3. The following diagnostic criteria must be met: bradykinesia AND at least ONE of the following: muscular rigidity, or resting tremor.

4b. A Screening DaT-SPECT, or a historical DaT-SPECT within 3 months of the Screening Visit (V1) that has been qualified by the central reader, shows evidence of dopamine transporter deficit per study requirements (refer to Section 4.2) and as determined by a central reader.

5a. Criterion removed.

6a. Study participant is in the  $\leq 2.5$  modified Hoehn and Yahr stage at Screening.

7a. Study participant has never taken medications for the treatment of motor symptoms of PD and is not expected to require starting ST with a high likelihood in the next 6 months as far as clinical judgement allows. These medications include:

- Levodopa
- Catechol-O-methyltransferase (COMT) inhibitors
- Dopamine agonists
- Monoamine oxidase-B (MAO-B) inhibitors
- Anticholinergic drugs
- Trihexyphenidyl
- Amantadine
- Safinamide

Exceptions to the above would be the following:

- Acute pharmacological testing for diagnostic purposes is allowed until 1 week before first Screening Visit.
- Historical treatment with symptomatic treatment (ST) for a duration of up to 1 month is allowed until 3 months before first Screening Visit (refer to details in exclusion criterion #26a).

8. Study participant has never taken part in disease-modifying treatment studies directed at NDD.

9. Study participant does not take N-acetyl cysteine or other cysteine donors or glutathione precursors on a regular basis as a food supplement.

10. Study participant is willing, competent, and able to comply with all aspects of the protocol, including follow-up schedule and biospecimen collection.

**Weight**

11. Study participant has a body mass index (BMI) of 16 to 34kg/m^2 (inclusive).

**Sex**

12. Contraception

---

- A male participant must agree to use contraception as detailed in Appendix 4 (Section 10.4) during the Treatment Period and for at least 90 days after the last dose of study medication and refrain from donating sperm during this period.
- A female participant is eligible to participate if she is not pregnant, not breastfeeding, and at least one of the following conditions applies:
  - Not a woman of childbearing potential (WOCBP) as defined in Appendix 4 (Section 10.4)

OR

A WOCBP who agrees to follow the contraceptive guidance in Appendix 4 (Section 10.4) during the Treatment Period and for at least 1 month after the last dose of study medication. The study participant must have a negative serum pregnancy test at Screening (Visit 1), which is to be confirmed negative by urine testing prior to the first dose of study medication at Baseline (Visit 3). If oral contraception is used, an additional barrier method will be required during the study as a study medication related-gastrointestinal upset or a drug interaction by CYR3A4 induction could interfere with efficacy.

## Informed consent

13. Capable of giving signed informed consent as described in Appendix 1 (Section 10.1.3) which includes compliance with the requirements and restrictions listed in the ICF and in this protocol.

## 5.2 Exclusion criteria

Participants are excluded from the study if any of the following criteria apply:

### Medical conditions

1. Study participant has any current or past medical or psychiatric condition that, in the opinion of the Investigator, could jeopardize or would compromise the study participant's safety or ability to participate in this study.
2. Study participant has a current history of alcohol or drug use disorder, as defined in the Diagnostic and Statistical Manual of Mental Disorders V, within the previous year before Screening.
3. Study participant has a known hypersensitivity to any components (and/or its excipients) of the study medication or comparative drugs as stated in the protocol.
- 4a. Study participant has a known relevant allergy (not including mild seasonal hay-fever and/or conjunctivitis or low-grade food intolerances), a pre-existing history of a relevant and clinically significant allergic condition, or a predisposition for an allergic reaction (eg, total immunoglobulin E value above normal range according to the study's central laboratory reference range) at Screening in the opinion of the Investigator.
5. Study participant wearing any kind of implantable device, including cardiac pacemakers, pumps, and implantable cardioverters, will be excluded from wearing the wearable sensor, but may participate in the main study.

---

6. Study participant with a known nickel allergy severe enough to preclude 24 hours a day/7 days a week wearing of a sensor device with a nickel alloy-containing housing will be excluded from wearing the wearable sensor, but may participate in the main study.
7. Study participants with any condition or in any circumstances that in the opinion of the Investigator, makes the participant inappropriate for wearing of the wearable sensor. These study participants will be excluded from wearing the wearable sensor but may participate in the main study.
8. Study participant has a brain magnetic resonance imaging (MRI) scan performed during Screening indicative of a clinically significant abnormality or a historical MRI scan during the 6 months before Screening Visit 1 of sufficient quality to show such abnormalities. In case of doubt, the significance is determined on a case-by-case basis in close collaboration with the Medical Monitor and should not include abnormalities like age-appropriate brain atrophy, minor white matter signals, or mild vasculopathy.
9. Study participant has any contraindication for the brain MRI or DaT-SPECT imaging.
10. Study participant has ongoing significant inflammatory gastrointestinal disorders and/or clinical signs of significant gastrointestinal problems at Screening. Study participants with PD-associated gastrointestinal motility problems need not be excluded.
11. Study participant has a MoCA score less than 23, indicating mild cognitive impairment or other significant cognitive impairment or clinical dementia at Screening that, in the opinion of the Investigator, would interfere with study evaluation.
12. Study participant has a lifetime history of suicide attempt (including an actual attempt, interrupted attempt, or aborted attempt), or has suicidal ideation in the past 6 months as indicated by positive responses ("Yes") to either Question 4 or Question 5 of the Columbia-Suicide Severity Rating Scale (C-SSRS) at Screening.
13. Study participant has a diagnosis of a significant CNS disease other than PD or history of epilepsy or seizure disorder other than febrile seizures as a child.
- 14a. Study participant has abnormalities in lumbar spine previously known or determined by a Screening lumbar x-ray (if conducted) that could preclude lumbar puncture, in the opinion of the Investigator. The participant must be excluded from lumbar puncture but not from study participation.
- 15a. Study participant has a history of clinically significant back pain, back pathology, and/or back injury (for example, degenerative disease, spinal deformity, or spinal surgery) that in the opinion of the Investigator is sufficiently severe as to potentially predispose participant to complications or technical difficulty with lumbar puncture. The participant must be excluded from lumbar puncture but not from study participation.
- 16a. Evidence or history of significant active bleeding or coagulation disorder or use of drugs that affect coagulation or platelet function within 14 days prior to lumbar puncture. The participant must be excluded from lumbar puncture but not from study participation.
- 17a. Allergy to lidocaine (Xylocaine®) or its derivatives. The participant must be excluded from lumbar puncture but not from study participation.

18a. Medical or surgical conditions which in the opinion of the Investigator represent a contraindication for lumbar puncture. The participant must be excluded from lumbar puncture but not from study participation.

19. Total bilirubin >upper limit of normal (ULN) ( $\geq 1.5 \times \text{ULN}$  total bilirubin if known Gilbert's syndrome). If study participant has elevations in total bilirubin that are >ULN and  $<1.5 \times \text{ULN}$ , fractionate bilirubin to identify possible undiagnosed Gilbert's syndrome (ie, direct bilirubin  $<35\%$ ).

20. Current or chronic history of liver disease, or known hepatic or biliary abnormalities (with the exception of Gilbert's syndrome or asymptomatic gallstones).

- Alanine aminotransferase (ALT), aspartate aminotransferase (AST), or alkaline phosphatase (ALP) are  $>1.5 \times \text{ULN}$ .
- For randomized study participants with a Baseline result  $>\text{ULN}$  for ALT, AST, ALP, or total bilirubin, a Baseline diagnosis and/or the cause of any clinically meaningful elevation must be understood and recorded in the eCRF.
- If the study participant has  $>\text{ULN}$  ALT, AST, or ALP that does not meet the exclusion limit at Screening, repeat the tests, if possible, prior to dosing to ensure there is no further ongoing clinically relevant increase. In case of a clinically relevant increase, inclusion of the study participant must be discussed with the Medical Monitor.
- Tests that result in ALT, AST, or ALP up to 25% above the exclusion limit may be repeated for confirmation. This includes reScreening.

21. Study participant has a history or present condition of respiratory or cardiovascular disorders at Screening (eg, cardiac insufficiency, coronary heart disease, uncontrolled hypertension, arrhythmia, tachyarrhythmia, or myocardial infarction) which is considered clinically significant by the Investigator.

22a. Study participant has medical history or current diagnosis of Type 1 diabetes or uncontrolled Type 2 diabetes. Well controlled type 2 diabetes in line with local clinical practice is acceptable.

23a. Study participant has clinically significant ECG abnormality at Screening, in the opinion of the Investigator. In addition, any study participant with any of the following findings will be excluded:

- QT corrected for heart rate using Fridericia's formula (QTcF) interval  $>450\text{ms}$  (in males) or  $>470\text{ms}$  (in females) in 2 of 3 ECGs.
- Bundle branch blocks (complete bundle branch block with  $\text{QRS} > 120\text{ms}$ ), marked right or left axis deviation or second and third degree atrioventricular block are excluded. Mild first degree atrioventricular block (defined as PR interval  $\leq 230\text{ms}$ ) is acceptable. Mild axis deviation, incomplete right bundle branch block ( $\text{QRS} \leq 120\text{ms}$ ), or left anterior hemiblock is acceptable if no underlying disease is suspected by the Investigator.

- c. Irregular rhythms other than sinus arrhythmia or occasional, rare supraventricular or rare ventricular ectopic beats.
- d. In the judgment of the Investigator, T-wave configurations that are not of sufficient quality for assessing QT interval duration.

24. Study participant has a history of recurrent unexplained syncopes or a family history of sudden death due to long QT syndrome.

25a. Study participant has had significant blood loss or has donated or received 1 or more units (450mL) of blood within 30 days prior to Baseline Visit, or has donated plasma or platelets within 14 days prior to Baseline Visit.

### **Prior/Concomitant therapy**

- 26a. Study participant has past history of use of medications for the treatment of motor symptoms of PD. Short (up to 4 weeks) past use of medications for the treatment of motor symptoms is permitted following a sufficient washout period. Medications included are: levodopa (maximum 400mg per day), dopamine agonists, MAO-B inhibitors, anticholinergics, or amantadine. A sufficient washout period is at least 3 months prior to the Baseline Visit.
- 27. Study participant received an investigational medicinal product (IMP), or has participated in another study of an IMP within a period of 90 days (or 5 half-lives of the drug, whichever is longer) before Baseline.
- 28. Study participant has had prior treatment with an investigational medical device, or participated in a study of an investigational medical device within a period of 90 days before Baseline.
- 29. Study participant has had prior treatment with an investigational vaccine, gene therapy, or stem cell therapy for PD (including active immunization or passive immunotherapy with monoclonal antibodies).
- 30a. Criterion removed.
- 31b.(1) Study participant has prior use of any of the following (drugs that may affect DaT-SPECT scan) within 50 days prior to Baseline: metoclopramide, alpha methyldopa, olanzapine, flunarizine, amoxapine, reserpine, bupropion, buspirone, cocaine, mazindol, methamphetamine, methylphenidate, norephedrine, phentermine, phenylpropanolamine, modafinil, clozapine.  
(2) Study participant has prior use of any of the following (drugs with possible Parkinson's disease-modifying effects) within 5 days prior to Baseline: pioglitazone, ambroxol, nilotinib, inosine, deferiprone, liraglutide, lixisenatide, N-acetylcysteine, phenylbutyrate, transdermal nicotine, exenatide, and isradipine.
- 32. Study participant has had prior treatment of PD involving intracranial surgery or implantation of a device (including deep brain stimulation).
- 33. Study participant has received prohibited prescription or nonprescription medicines (Section 6.5.2) (including over-the-counter medicines and herbal and dietary supplements [including St John's Wort]) that have been taken within 14 days prior to Baseline.

## **Prior/Concurrent clinical study experience**

34. Participant has previously participated in this study or participant has previously been assigned to treatment in a study of the medication under investigation in this study.

## **Diagnostic assessments**

35a. Positive prestudy medication/alcohol/recreational drug screen, unless reasonably explained by concomitant use of a medication.

36. Positive human immunodeficiency virus antibody test.

37. Presence of hepatitis B surface antigen at Screening.

38. Positive hepatitis C antibody test result at Screening or within 3 months prior to starting study medication. NOTE: Participants with positive hepatitis C antibody due to prior resolved disease can be enrolled, only if a confirmatory negative hepatitis C ribonucleic acid (RNA) test is obtained.

39. Positive hepatitis C RNA test result at Screening or within 3 months prior to first dose of study medication. NOTE: Test is optional and participants with negative hepatitis C antibody test are not required to also undergo hepatitis C RNA testing.

- The hepatitis C antibody test is a standard test used at Screening to determine eligibility, and hepatitis C RNA testing is optional and only performed when the antibody test is positive in order to consider participants with positive hepatitis C antibody test for enrollment into the study. Where hepatitis C RNA testing is unavailable, a positive hepatitis C antibody test will be used for exclusion.
- NOTE: Stable chronic liver disease (including Gilbert's syndrome and asymptomatic gallstones) is acceptable if the participant otherwise meets entry criteria.

40b. Study participant has medical history or current diagnosis of renal impairment and/or Screening laboratory results show any of the following confirmed by repeat test:

- Criterion removed.
- Abnormal urinalysis considered clinically significant by the Investigator, eg, red cell casts or hematuria in microscopy.  
Abnormal urinalysis may be treated during the Screening Period and retested prior to Baseline, providing that study participants are still within the Screening Period window and the treatment medication is stopped 14 days prior to Baseline.
- Results for urine test of albumin/creatinine ratio of  $\geq 30\text{mg}/\text{mmol}$ .
- Study participants with evidence of urinary tract infection during the Screening Period.  
Urinary tract infection may be treated during the Screening Period and retested prior to Baseline, providing that study participants are still within the Screening Period window and the treatment medication is stopped 14 days prior to Baseline.

- e. The estimated glomerular filtration rate of <45mL/min/1.73m^2 (using the Chronic Kidney Disease Epidemiology Collaboration formula).
- f. Clinically significant electrolyte abnormalities.

41. History of significant renal disease.

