### 1.3 Schedule of Activities

Day	Screening		Treatment															SFU
	V1	V2 a	V3	V4 b	V5	V6	V7 b	V8	V8a w	V9	V10	V11	V12	V13	V14	V15	V16 b	
			BL		M1	M2	M3	M4	M5	M6	M8	M10	M12	M14	M16	M18 EOT	M19	
	-42 to -23		-21 to -14	0	10 +/-1	30 +/-1	60 +/-3	90 +/-3	120 +/-5	150 +/-5	180 +/-5	240 +/-5	300 +/-5	360 +/-5	420 +/-5	480 +/-5	540 +/-5	570 +/-5
Written Informed Consent incl. genetics ICF and wearable sensor ICF	X																	
Demographics, PD history	X																	
General medical and procedure history	X																	
Inclusion/Exclusion criteria	X	X	X															
Withdrawal criteria c				X	X	X	X	X	X	X	X	X	X	X	X	X		
Participant identification card assignment				X														
Prior and concomitant medications and procedures	X	X	X	X	X	X	X	X	X	X	X	X	X	X	X	X	X	
Height	X																	

Day	Screening		Treatment														SFU																							
	V1	V2 a	V3	V4 b	V5	V6	V7 b	V8	V8a w	V9	V10	V11	V12	V13	V14	V15	V16 b																							
	BL				M1	M2	M3	M4	M5	M6	M8	M10	M12	M14	M16	M18 EOT	M19																							
				 / 			 / 																																	
	-42 to -23	-21 to -14	0	10 +/-1	30 +/-1	60 +/-3	90 +/-3	120 +/-5	150 +/-5	180 +/-5	240 +/-5	300 +/-5	360 +/-5	420 +/-5	480 +/-5	540 +/-5	570 +/-5																							
Vital signs, weight d	X	X	X	X	X	X	X	X		X	X	X	X	X	X	X																								
Adverse events e	X	X	X	X	X	X	X	X	X	X	X	X	X	X	X	X																								
Physical examination	X		X			X							X			X																								
Brief physical examination f		X		X	X		X			X	X	X		X	X		X																							
Neurological examination (incl. modified H&Y)	X	X g				X								X			X																							
Brief neurological examination (incl. modified H&Y) h			X	X	X		X	X		X	X	X		X	X		X																							
MRI		X i																																						
DaT-SPECT		X j												X k			X																							
CSF sampling l		X												X			X																							
12-lead ECG m	X	X	X	X	X	X	X			X		X	X		X	X	X																							
Blood sampling for chemistry, hematology, coagulation	X		X	X	X	X	X	X	X	X	X	X	X	X	X	X	X																							
Cystatin C	X		X	X	X	X	X	X		X	X	X	X	X	X	X	X																							

Day	Screening		Treatment															SFU												

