## 2.3 Benefit/Risk assessment

To date, there are no approved 'neuroprotective' and/or 'disease-modifying' treatments to stop or slow disease progression of PD, which remains a large unmet medical need.

UCB0599 acts at an early-stage of ASYN aggregation by inhibiting the initial nucleation event or seed formation by inhibiting misfolding; therefore, it may halt the progression of PD vs only treating the symptoms. The outcome of this study will support the development of a medication that may provide a potential benefit for patients with PD.

Drug hypersensitivity is an important identified risk. Other potential risks include: hepatotoxicity (based on clinical data) and cardiac effects. Renal laboratory abnormalities are also kept under close safety monitoring.

In Phase 1 development of UCB0599, 5 studies (UP0030, TM0017, UP0023, UP0077, and UP0078) demonstrated that UCB0599 has acceptable safety, PK and tolerability profiles for further clinical development. Overall, the majority of treatment-emergent adverse events (TEAEs) were mild or moderate in intensity and resolved. In UP0030, 2 events of hypersensitivity were reported. An additional 2 events of hypersensitivity occurred in study participants who received UCB0599 in UP0077. A causal relationship between the reported events of drug hypersensitivity and UCB0599 is considered plausible. The hypersensitivity reactions are further described in the IB.

There have been no reports of anaphylaxis in the UCB0599 clinical program.

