## 8 STUDY ASSESSMENTS AND PROCEDURES

The order of assessments is optimized for consistency, logistic requirements by the site, and minimized participant burden. Slight variations among the sites do not constitute a protocol deviation, while sites are encouraged to keep the order of assessments consistent over time. As a general rule, all assessments with a high likelihood of being sensitive to previous intake of ST need to be conducted in a practically defined off-state (as defined in Section 6.5.3) before intake of ST is resumed. To avoid bias and to maintain consistency over time, this rule should also apply to participants not (yet) on ST. The assessments in the timeslot preceding intake of ST should comprise:

- PROs (at home prior to a clinic visit or first assessments at the clinic)
- MDS-UPDRS (all parts)
- Virtual Motor Exam (VME) (after a period of rest)
- ECGs
- Laboratory and PK blood sampling
- Vital signs

Study procedures and their timing are summarized in the Schedule of Activities (Section 1.3).

Protocol waivers or exemptions are not allowed.

Immediate safety concerns should be discussed with the Sponsor immediately upon occurrence or awareness to determine if the participant should continue or discontinue study medication.

Adherence to the study design requirements, including those specified in the Schedule of Activities (Section 1.3), is essential and required for study conduct.

All Screening evaluations must be completed and reviewed to confirm that potential participants meet all eligibility criteria. The Investigator will maintain a Screening log to record details of all participants screened and to confirm eligibility or record reasons for Screening failure, as applicable.

Procedures conducted as part of the participant's routine clinical management (eg, blood count) and obtained before signing of the ICF may be utilized for Screening or Baseline purposes provided the procedures met the protocol-specified criteria and were performed within the time frame defined in the Schedule of Activities.

The maximum amount of blood collected from each participant will not exceed 50mL at any visit and will not exceed 510mL over the duration of the study, including any extra assessments that may be required. Repeat or unscheduled samples may be taken for safety reasons or for technical issues with the samples.

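### Exclusion 20 and the note under exclusion 39 disagree on whether a stable chronic liver disease other than Gilbert's syndrome or asymptomatic gallstones is acceptable; criterion 20 should be stated to govern

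*Protocol*

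**What the plan says.** Protocol 5.2 deals with liver disease in two places, both current text.

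- Criterion 20, under Medical conditions, excludes anyone with "Current or chronic history of liver disease, or known hepatic or biliary abnormalities (with the exception of Gilbert's syndrome or asymptomatic gallstones". The bracket ends there and nothing else is exempted.
- The second bullet under criterion 39, under Diagnostic assessments, follows the hepatitis C testing rules and reads: "NOTE: Stable chronic liver disease (including Gilbert's syndrome and asymptomatic gallstones) is acceptable if the participant otherwise meets entry criteria".

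Three general rules bear on how the two fit together. Section 5.2 opens with "Participants are excluded from the study if any of the following criteria apply". Section 5 adds "Prospective approval of protocol deviations to recruitment and enrollment criteria, also known as protocol waivers or exemptions, is not permitted", and Section 8 repeats "Protocol waivers or exemptions are not allowed".

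Section 2.3 explains why liver eligibility matters here: "Other potential risks include: hepatotoxicity (based on clinical data) and cardiac effects".

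**The concern.** The two sentences cover the same subject with different scope. In criterion 20 the exceptions form a closed list. In the note the same conditions follow the word *including*, so they illustrate a wider class. No section says which sentence prevails.

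What is at stake is consistent application of a safety eligibility rule. A site that relies on the note could enrol someone with another stable liver disease, while a site that relies on criterion 20 would refuse the same kind of patient. The sponsor treats the liver as a live safety question. Protocol Amendment 5 added a Month 5 visit for liver function tests, and SAP Amendment 4 added four liver function outputs. Unrecognised liver disease at entry makes a later liver signal in an individual harder to attribute.

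**Working it through.** No arithmetic decides this point, and no stated sample size, power or error rate depends on it. The check is to take each kind of participant through both rules.

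| Participant | Criterion 20 | Note under 39 | Result |
|---|---|---|---|
| Gilbert's syndrome | exempt | acceptable | agree |
| Asymptomatic gallstones | exempt | acceptable | agree |
| Another stable chronic liver disease, all laboratory tests within limits | excluded | acceptable, if entry criteria are otherwise met | conflict |
| Another liver disease, not stable or outside a laboratory limit | excluded | not covered | agree |

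**Which rule prevails in the third row.** If *otherwise* means apart from the liver disease, which is its natural sense, the two rules contradict each other. If it means that every entry criterion must be met, criterion 20 included, the participant is excluded. The opening sentence of 5.2 and the bar on waivers support the second reading. On that reading, however, the note accepts nobody whom criterion 20 does not already exempt, so its general wording has no effect except to mislead.

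**How wide the third row is.** A person in it must also pass:

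- the bilirubin limit (criterion 19);
- the 1.5 × ULN limits on ALT, AST and ALP (criterion 20);
- the hepatitis B and C tests (criteria 37 to 39);
- the investigator's judgement under criterion 1.

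The documents give no count or prevalence for this group.

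**Whether the analysis is touched.** SAP Appendix 6 (6.6) removes participants from the FAS on five criteria: 1a, 2a, 4b, 6a and 7a. None concerns the liver, so a breach of criterion 20 does not change FAS membership.

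**What monitoring is in place.** The row "Blood sampling for chemistry, hematology, coagulation" in Protocol 1.3 gives these on-treatment visits after Baseline:

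- Day 10 and Months 1, 2, 3, 4 and 6: 6 visits
- Months 8, 10, 12, 14, 16 and 18: 6 visits
- Regular total: 6 + 6 = 12

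Visit 8a (Month 5) also carries chemistry, but the protocol says that it is conducted as an unscheduled visit. It came in with Amendment 5 (30 Jun 2023), so anyone already past Month 5 by then would not have had it.

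**What is recorded at entry.** For a Baseline liver test above ULN, criterion 20 requires that "a Baseline diagnosis and/or the cause of any clinically meaningful elevation must be understood and recorded in the eCRF". With normal tests that requirement does not apply, and a pre-existing liver disease would appear only in the medical history.

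**The case against.** The strongest reply is that the protocol answers the question itself. One exclusion is enough, waivers are barred, and the note is conditional on the entry criteria. The note also sits directly after the hepatitis C rules and names exactly criterion 20's two exceptions. It can be read as saying only that the viral tests do not themselves exclude such people. This largely stands. It makes criterion 20 the better-supported rule, and a reader should not infer that sites are free to choose. It does not make the note harmless, because its plain words accept a class that criterion 20 bars, and a coordinator may reach the note without arguing back to criterion 20.

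The second reply is that the harm is hypothetical and the safeguards are strong. This also stands. The documents show no affected participant and no site query. Besides the visit schedule, there is an etiological work-up at the liver stopping criteria (Protocol Table 10-1), adjudication of potential drug-induced liver injury cases (SAP 6.1.6) and a randomized placebo arm. A reader might infer that liver findings could not be interpreted, or that ineligible patients were enrolled. The documents support neither.

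The third reply is that new wording may come too late. Enrolment status is not stated. SAP Amendment 4 (21 Oct 2024) already describes how many participants started symptomatic treatment before Month 12, so enrolment may well be complete. That moves the remedy from the protocol text to the handling of deviations, but does not remove it.

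**Conclusion.** The inconsistency is real but minor. Criterion 20 governs on the better reading. The note under 39 should not be left saying something broader in a trial of a drug with a named hepatotoxicity risk.

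That the group is probably small is a judgement from the other liver criteria, not a figure in the documents. Power and the FAS are unaffected. So is the primary estimand, provided that a liver-history deviation is not treated as an intercurrent event. SAP 1.2 leaves that classification to the protocol deviation specification, which is not among these documents and may already settle the matter.

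A reader might also infer that, because the note called such people acceptable, counting them as eligible is as defensible as counting them as deviations. The text does not support that: the any-one-criterion rule and the bar on waivers point to a deviation.

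**What to change.** Delete the note under criterion 39, or limit it to Gilbert's syndrome and asymptomatic gallstones with a cross-reference to criterion 20. This changes one sentence.

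If enrolment is complete, state before unblinding that criterion 20 governs. Then:

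- record any participant enrolled with another chronic liver disease as an inclusion/exclusion deviation, a category that SAP 5.1.2.2 already has;
- say in the same entry that the deviation is not an intercurrent event for efficacy;
- identify the participant in the liver outputs of SAP 5.4.3.1.1, using the coded medical history of SAP 6.1.3.

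This costs one entry in the protocol deviation specification and one flag from data already collected. If the specification already covers the case, a single check closes the point.
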